Q2: What are the moderators and mediators of the effectiveness of Concussion Coach?

- (a) Is comfort with technology related to efficacy of Concussion Coach?
- (b) Is perceived social support related to efficacy of Concussion Coach?

Q3: Does use of Concussion Coach (a) increase Veterans' knowledge about TBI and change Veterans' attribution of symptoms from mild TBI to less "pathological" explanations (e.g., stress, post-deployment re-adjustment, or other causes), (b) increase Veterans' self-efficacy in coping with symptoms?

More broadly, are the effects of Concussion Coach on PCS and psychological distress mediated through change (from T1 to T2) in Veterans' perceptions and knowledge of the illness and in self-efficacy?

Q4: What aspects of Concussion Coach are most associated with positive outcomes among recipients of Concussion Coach? Is more frequent use of specific components of Concussion Coach associated with greater improvement, relative to other components?

Q5: What are the factors associated with use of Concussion Coach or with deriving benefit from use of Concussion Coach that can be used to inform future modifications of the application and wide scale implementation?

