5.0 Study Procedures

5.1 Study Design

- Describe experimental design of the study. Include sequential and/or parallel phases of the study, including durations, and explain which interventions are standard of care.
- Include a description of how anticipated risk will be minimized and include an analysis of risk vs. potential benefit.
- Provide description of the study population (delineate all categories of subjects – patients, providers, family members, employees, etc.). Include anticipated enrollment numbers
- As applicable, provide information on any added protections for vulnerable populations.
- If applicable include information on data.

Patients who meet eligibility criteria and consent to participate in the study are randomly assigned to one of two arms, either the Concussion Coach group, which will receive the Concussion Coach "Explorer" version either downloaded onto their own smart phone or via an iPod touch® given them for this purpose or the no mobile app control group. Study personnel will explain the purpose of the study, complete the informed consent process in person or over the telephone, obtain the random treatment assignment and introduce the participant to his/her baseline evaluator, if appropriate. The random assignment to intervention will be accomplished in blocks within each site. While small block sizes allow intervention group sizes to be very similar it may make the allocation process predictable. Therefore, to reduce selection bias and achieve balance across the intervention arms, a sequence list of individual assignments by random block sizes will be generated.

Both groups will be assessed in a pre/post intervention design and will be compensated for completing study questionnaires. During the time that they are involved in the study, the intervention group will be sent (via Concussion Coach) reminders to engage with the App. Their use (e.g., total time spent on each component of the App) will be collected electronically. Both

Version:13 05/31/2018

groups will receive care as usual (meaning their regularly scheduled VA appointments and medications). At the completion of the study, both groups will be encouraged to download the App for their own use, with assistance from the study team if needed (see Figure 2).

Description of Intervention & Training

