Data Collection Methods: After informed consent and randomization, participants will complete baseline study measures. At follow-up, participants will be re-assessed using the same measures via mail, telephone or in person with telephone reminders, if needed. In addition, Concussion Coach will also collect the extent of their interaction with the application during their participation.

Individual interviews will be conducted with at least 10% of the Concussion Coach users to evaluate their perception and satisfaction with other TBI-related education received within the VA to date, their overall satisfaction with Concussion Coach e.g. its ease of use, perceived barriers and facilitators to the use of the App, behavioral intention to use Concussion Coach in the future and recommendations for improving it. This 10% sample will not be random – rather we will solicit interviews from those who improved using PCS Concussion Coach, those who did not get better or became worse, and those who did not use the App during the study period or used it infrequently. In addition to qualitative questions about barriers and facilitators, interview questions will include quantitative assessment of satisfaction (e.g., rating scales of satisfaction). Interviews will be conducted by experienced trained interviewers (e.g., [name]) and will be audio recorded. Participants will already be consented in person or over the telephone, so the interviewer will identify and briefly recap the consenting process, the project, and then ask permission for audio tape recording the interview. Interviews will be conducted by phone or in person based on participant convenience. The interviewer will use standard communication techniques to stimulate discussion such as generic prompts (tell me more), summarizing statements, silence, and eye contact. If the respondent exhibits adverse reactions, such as shame, during the interview, every effort will be made to encourage him or her and they will be reminded of their rights as participants.

Risk Minimization Plan:

The educational program is self-administered and participation is strictly voluntary. There are no known risks involved. The PI will inform participants of all methods used to maintain confidentiality of information. Participants will be assured of the confidentiality of the data and that no one outside of the research team will have access to the raw data.

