5.5 Study Evaluations

Table 1 outlines quantitative measures we propose to use. Examination of potential mediator and moderator variables will allow us to determine who is most likely to benefit from the intervention (e.g., people with limited social support, people who are less 'tech savvy') and qualify our findings. Justification for each of these included variables is contained in the description of each measure below the table.

Table 1. Study Measures

Construct	Tool	Timepoint
Primary Outcomes		
PCS	Neurobehavioral Symptom Inventory (NSI)	Baseline, up to 1 year later
Symptom Exaggeration	mBias	Baseline, up to 1 year later
Psychological Distress	Brief Symptom Inventory (BSI) PCL-5 Strong Star (PCL)	Baseline, up to 1 year later

Time Spent on Concussion Coach in total and on various components	Concussion Coach download	Duration of study i.e. a 3 month period for use of APP
PCS	NSI from Concussion Coach download (could be multiple NSIs depending on subject)	Duration of study i.e. a 3 month period for use of APP
Barriers and Facilitators of Concussion Coach use and effectiveness	Concussion Coach Interview Follow-Up Data Form	Up to 1 year later for Follow-Up Form. Interview date is an undetermined time after the final study visit.
Potential Mediators		
Perceptions and Knowledge of Illness	TBI Education Satisfaction, Knowledge, and Attributions	Baseline, up to 1 year later
Self-Efficacy	Self Efficacy for Symptom Management Scale (SEsx)	Baseline, up to 1 year later
Potential Moderators		
Social Support	Social Support Questionnaire – Short Form (SSQSR)	Baseline, up to 1 year later
Comfort with Technology	eHealth Literacy Scale (eHEALS)	Baseline, up to 1 year later
Use of Apps during study period	Follow-Up Data Form	Up to 1 year after Baseline
Mental Health Treatment during study period	Follow-Up Data Form	Up to 1 year after Baseline
Demographics, Health and Disability Status		
Age, gender, diagnosis, comorbidities, other injuries.	Medical Record: Participant Information Form Enrollment Participant Information Form	Baseline

Primary Outcome Measures:

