Hypothesis 2: The effects of TBI Coach on PCS (and psychological distress) will be greater for Veterans who have (a) greater comfort with technology at baseline than for those who are less comfortable; (b) greater social support at baseline than for those with less social support.

Analysis: Two separate tests of moderated effects of TBI Coach will be performed with respect to each outcome. Each regression model in H1 (one per outcome) will be extended by adding a 2-way interaction term (between intervention and (a) eHealth Literacy Scale and (b) Social Support score; one at a time (i.e. two different moderation models per outcome). A significant coefficient of an interaction term will indicate presence of interactive effects. A co-plot using model fitted values will also be produced to further investigate the nature of any significant interaction.

Hypothesis 3: If TBI Coach improves Veterans' (a) knowledge about TBI and attribution of symptoms and/or (b) self-efficacy in coping with symptoms, Veterans will have less PCS and Psychological Distress.

Analysis: Single-mediator models⁷³ will test the indirect effects of the group variable (TBI Coach) on each outcome (separately) with respect to mediating variables: (a) knowledge and attribution, and (b) self-efficacy. Preliminary regression analyses will test whether (1) TBI Coach substantially changes the mediating variable, and (2) the mediating variable changes the outcome. Next, we will proceed to a full mediation model with simultaneous estimation of both direct and indirect effects of TBI Coach on the outcome. The mediated effect will be estimated as a product of the two path coefficients alpha and beta in the indirect pathway. The distribution of the product of coefficients is non-normal and this has implications for statistical inference as well as power calculation (see section on sample size justification). Therefore, the analysis will

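### Hypothesis 3 measures mediators and outcomes at the same two assessments, so it can support an association consistent with mediation but cannot show that the mediator changed the outcome

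*Combined protocol and SAP*

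**What the plan says.** Section 5.1 sets out two assessments: "Both groups will be assessed in a pre/post intervention design". Under its data collection methods it adds: "At follow-up, participants will be re-assessed using the same measures via mail, telephone or in person with telephone reminders, if needed".

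Table 1 in section 5.5 gives the NSI, the BSI and PCL-5, the knowledge and attributions questionnaire and the self-efficacy scale one and the same schedule: "Baseline, up to 1 year later". Research question Q3 in section 2.0 frames mediation as acting through T1-to-T2 change in the mediators, which is the same window as the outcome.

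The Hypothesis 3 analysis in section 5.6 starts with two regressions: "Preliminary regression analyses will test whether (1) TBI Coach substantially changes the mediating variable, and (2) the mediating variable changes the outcome". It then fits single-mediator models in one direction (app to mediator to outcome), estimates the mediated effect as the product alpha × beta, and bases inference on a Bayesian percentile interval. The reason given for the Bayesian method is the non-normal distribution of the product. The section has no reversed model, no sensitivity analysis for temporal order, and no caveat that the mediator-outcome path is associational.

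**The concern.** Randomisation protects the path from app to mediator and the total effect of the app on symptoms. It does not protect the path from mediator to outcome. When both are taken at T2, that path is a partial association, and it looks the same whether self-efficacy lowers symptoms or lower symptoms raise self-efficacy.

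The second direction is not far-fetched. The self-efficacy scale asks about confidence in managing symptoms. Section 2.0 itself says that the presence of acute symptoms can strengthen patients' expectations and beliefs.

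At stake is the explanation of why the app works and which part of it to strengthen. Adjusting for the baseline outcome does not settle what happened between T1 and T2, and neither does adjusting for the baseline mediator.

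**Working it through.** **The plan's own figures.** Section 5.6 gives N = (20 × 33 + 150) × 0.60 × 0.80 = 388.8, used as 388.

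It also gives Sobel power of 0.82, with a = b = 0.14, predictor and mediator SD 0.5, squared correlation 0.3 and error SD 0.2:
- Variance term: 0.0196 × 0.04 / (0.25 × 0.7) + 0.0196 × (0.25 × 0.7) / 0.25 = 0.00448 + 0.01372 = 0.0182, with square root 0.1349.
- t = 0.0196 × √388 / 0.1349 = 2.86.
- Two-sided power = Φ(2.86 − 1.96) = 0.816.

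The figure reproduces. It takes the mediator-to-outcome direction as given, so it does not bear on this point.

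**Set-up of the check (assumed, not from the documents).** N = 388, 1:1, and the mediator has no effect on the outcome.
- T2 outcome: Y = 0.6·Y0 − d·arm + error (SD 0.8). Its within-arm SD is √(0.36 + 0.64) = 1, so d is in SD units.
- T2 mediator: M = 0.4·M0 − g·Y + error (SD 0.7), where g is the reverse path.
- Fitted models: M on arm, Y0 and M0 (alpha); Y on arm, M, Y0 and M0 (beta). Adjusting for M0 is generous to the plan, because section 5.6 names only the baseline outcome.
- A 95% Monte Carlo interval for alpha × beta stands in for the planned Bayesian interval.

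**Expected false credit, in closed form.** alpha = g·d and beta = −0.64g / (0.64g² + 0.49). The share of the app effect credited to the mediator is therefore 0.64g² / (0.64g² + 0.49):
- g = 0.2: 0.0256 / 0.5156 = 5%
- g = 0.3: 0.0576 / 0.5476 = 10.5%
- g = 0.5: 0.16 / 0.65 = 24.6%

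**How often the interval excludes zero (true mediated effect zero).**

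| App effect d | g = 0.3 | g = 0.5 |
|---|---|---|
| 0.2 SD | 13% | 22% |
| 0.3 SD | 22% | 44% |
| 0.4 SD | 33% | 68% |

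At g = 0.2 the rate runs from about 8% to 18% over the same app effects. Repeat runs moved individual cells by a few percentage points.

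**A second data-generating model** (symptoms and mediator evolving over two intervals, 2,000 runs per cell) gave, for g = 0.2, 0.3 and 0.5:
- d = 0.2: 6.6%, 11.4%, 24.8%
- d = 0.3: 13.0%, 19.7%, 41.6%
- d = 0.5: 26.0%, 47.9%, 86.0%

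The share wrongly credited was about 4%, 8–9% and 20%. Preliminary step (2) was significant in 97% to 100% of runs once g was at least 0.2, although the mediator did nothing. With g = 0 the interval excluded zero in at most 0.2% of runs, and with d = 0 in at most 5.4%. False credit above the nominal level therefore needs both an app effect and a reverse path.

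**Can the T2 data tell the directions apart?** In the first set-up the mediator-outcome residual correlation under reverse causation is −0.8g / √(0.64g² + 0.49). That is −0.24 / 0.740 = −0.32 at g = 0.3 and −0.40 / 0.806 = −0.50 at g = 0.5. Simulated true forward mediation gave about −0.32 to −0.49, which is practically the same. The reversed model (app to symptoms to mediator) was also significant in 19% to 76% of runs when forward mediation was true.

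**The case against.** Several points on the other side are fair.

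- Aim 2 in section 3.0 speaks of exploring mediation, and section 2.0 gives a prior basis for the planned direction in social cognitive theory. Two-wave mediation always has this limit. This stands as context. However, Hypothesis 3 is printed under Aim 3, which sets out to determine what works, and section 5.6 says mediation has the most stringent sample size requirement. Neither point supports the causal wording of step (2).
- The app effects and reverse paths are assumptions, and the scenario is one-sided: all reverse effect and no forward effect. This stands. The results show what could happen, not what will.
- The planned model estimates direct and indirect effects together, so with 10% to 25% falsely credited a reader would still see most of the effect as direct. This stands and limits the harm.

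Three stronger readings are tempting, and the material does not support them. A reader might infer that Hypothesis 3 will be confirmed whenever Hypothesis 1 is. Among simulated trials with a significant Hypothesis 1, false mediation appeared in 16% to 68%, and in more than half in only one of the six settings tabulated. A reader might infer that nothing is measured between T1 and T2. Table 1 does list in-app NSI readings, possibly several per user, but they are outcome data from one arm. A reader might extend the argument equally to both mediators. There is no evident reason why feeling better should raise factual knowledge about TBI, so the argument applies mainly to self-efficacy and attributions.

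**Conclusion.** The concern holds as a limit on what Hypothesis 3 can claim. Section 5.6 states a directional test that its measurement schedule cannot deliver, and it would read an indirect-effect interval excluding zero as a mediated effect. The sizes in the tabulated set-up rest on N = 388, app effects of 0.2 to 0.4 SD, reverse paths of 0.2 to 0.5 and a true mediated effect of zero. None of the effect sizes or reverse paths comes from the documents. If symptom relief does not move the mediator, or the app has no effect on symptoms, the problem does not arise beyond about the nominal 5%. The randomised comparison in Hypothesis 1 is untouched. This is worth correcting before analysis, but it does not threaten the trial's main result.

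**What to change.** In the Hypothesis 3 analysis of section 5.6:

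1. Change step (2) so that it tests whether the mediating variable *is associated with the outcome at T2*. State that Hypothesis 3 results will be reported as *consistent with mediation*, not as evidence of direction.
2. In the same Mplus model, refit with the T2 mediator-outcome residual correlation fixed over a grid. Pre-specify the grid for each mediator, with its sign set by that mediator's scoring. Report the value at which the indirect-effect interval first includes zero. Present this as a description of robustness and not as a pass/fail rule, because genuine mediation and reverse causation gave the same residual correlations above.
3. If the reversed model is shown, show it as description only. It must not be used to decide direction.

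The cost is a few extra runs of models already planned, and more cautious Hypothesis 3 conclusions.

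A mid-study assessment is not proposed. The Abstract reports 419 participants enrolled (93% of goal), so it would miss most of them. Measuring only the mediator mid-study would not be enough either: in the second model false mediation then still appeared in 4.1% to 52.0% of runs in cells with both an app effect and a reverse path. It fell to 0.0% to 2.0% only when mid-study symptoms in both arms were also measured and adjusted for.

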3.0 Objectives

The proposed study is a 4-year randomized control trial investigating the utility of an interactive, self-management smartphone application, "Concussion Coach," one of a suite of mobile applications developed by VA. The primary goal of the proposed study is to evaluate the efficacy of Concussion Coach for improving clinical outcomes in those with a history of mild traumatic brain injury (mild TBI) and to determine what aspects of Concussion Coach are most

useful to Veterans. An overarching goal of this line of research is to improve access among Veterans with mild TBI who still have symptoms months to years after injury.

Aim 1. Evaluate the efficacy of Concussion Coach for improving clinical outcomes among recipients of Concussion Coach.

Hypothesis 1 (Primary Hypothesis): Patients randomized to receive Concussion Coach for 3 months will have (a) lower Post-Concussion Symptom severity (PCS) and, (b) lower psychological distress, compared to patients randomized to a no intervention control group, after adjusting for baseline severity and other potential confounders.

Aim 2. Explore mediation/moderation of Concussion Coach effects on clinical outcomes among recipients of Concussion Coach.

Hypothesis 2: The effects of Concussion Coach on PCS (and psychological distress) will be greater for Veterans who have (a) greater comfort with technology at baseline than for those who are less comfortable; (b) greater social support at baseline than for those with less social support.

Aim 3. Determine the aspects of Concussion Coach most associated with positive outcomes.

Hypothesis 3: If Concussion Coach improves Veterans' (a) knowledge about TBI and attribution of symptoms and/or (b) self-efficacy in coping with symptoms, Veterans will have less PCS and psychological distress.

Aim 4. Obtain qualitative information on factors associated with use of Concussion Coach or with deriving benefit from use of Concussion Coach that can be used to inform future modifications of the application and wide scale implementation.

Hypothesis 4: More time spent on (a) Concussion Coach use, and (b) specific interactive components of Concussion Coach (i.e., the "tools" section) will be associated with lower PCS symptom severity after adjusting for baseline PCS values and potential confounders.

Research Question 1: What barriers prevent patients from using the Concussion Coach and from improving on PCS symptom severity?

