 of 22 PCS that is used broadly throughout VA, DoD, and civilian settings. Users are
 provided with interpretive feedback about the severity of their symptoms and information
 about their score relative to the last administration. Repeated self-assessment can be
 viewed in graphical form. Users can also schedule future assessments and reminders to
 complete the NSI.
- Portable skills are available to address the Veteran's symptoms, regardless of etiology. The
 user identifies and rates the distress from a list of symptoms. Depending on the problem and
 the severity, the user is routed to any of a number of helpful skills depending on the
 symptom and severity; the user is then asked to rate his/her distress following use of the
 stress management tool. Feedback and recommendations are provided based on the

change in score. Irritability, sleep problems, memory problems, and headaches are the four foci of this app. If a symptom is rated 9 or 10, crisis strategies are provided.

Training: Concussion Coach will be publicly available just as is the PTSD Coach. To facilitate its use, the developers will create a brief handout to provide basic instructions on its use. [name], the primary author of both the PTSD Coach and the Concussion Coach, will be responsible for this content. Therefore, we are testing Concussion Coach as it will be implemented outside of this trial, increasing applicability of our findings to the "real world."

Safety Plan: If participants voice suicidal ideation/plan either in person or via telephone to study staff, hospital policy will be followed. There are specific policies in place for crisis management both via telephone and in person. All research personnel with participant contact will be trained per this policy. In addition, interviewers and research assistants will be trained by the PI on how to identify and respond to participants in distress. This will occur through role play, readings, and other pre-study group trainings. All proposed pertinent study personnel have clinical training/experience and suicide/violence assessment experience. They will follow VA Suicide Prevention guidelines and are required to have had all VA research trainings which include Suicide Prevention guidelines.

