be performed using the Mplus statistical application which offers alternatives that do not require the regular assumption of symmetric, normal distributions for parameter estimates. Bayesian estimation method with diffuse priors will be used with appropriate posterior simulation schemes based in Markov Chain Monte Carlo (MCMC) methods. One advantage of the MCMC estimation process is that it provides accurate tests of mediated effects for small samples; e.g. by simply taking the product of the two coefficients alpha and beta for every draw and compute its standard deviation across all draws to obtain standard errors of mediated effect. Also, unlike the normal-based ML confidence interval, inference will rely on Bayesian credibility interval based on the percentiles of the posterior, which easily allows for a strongly skewed distribution alphabeta product⁷⁴

Hypothesis 4: More time spent on (a) TBI Coach use, and (b) specific interactive components of TBI Coach (i.e., the "tools" section) will be associated with lower PCS symptom severity after adjusting for baseline PCS values and potential confounders.

Analysis: A regression model of PCS will be performed on the TBI Coach sample only, separately for (a) TBI coach use, and (b) each interactive component as the main predictor. First the PCS baseline score, demographics and other potential confounders will be included in the base model. Then a full model with addition of the time score for one TBI Coach aspect at a time will be fitted. Appropriate transformation (e.g. log) of all time variables will be done as suggested by their general distribution; a significant negative coefficient of the time variable will confirm a negative association between time spent on that component and symptom severity. Standardized coefficient estimates as well as R-sq estimates will be obtained so that all TBI Coach aspect-specific models can be compared on the relative strengths of the aspect-outcome relationships.

As an extension, secondary analysis will be performed on the TBI Coach components that show strong relationship in the expected direction. Each time spent (as a dependent variable) will be regressed on the predictors in the base model to identify both positive and negative contributory factors to the specific component usage.

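### H4(b) makes its prediction for the tools section, but the analysis tests each interactive component without adjustment and names no model that decides the hypothesis

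*Combined protocol and SAP*

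**What the plan says.** Section 3.0 (Objectives) and section 5.6 (Data Analysis) word Hypothesis 4(b) alike apart from the app's name. The Objectives have "specific interactive components of Concussion Coach (i.e., the 'tools' section) will be associated with lower PCS symptom severity" and the analysis section has "specific interactive components of TBI Coach (i.e., the 'tools' section) will be associated with lower PCS symptom severity". Both equate the interactive components with the tools section.

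The H4 analysis in section 5.6 uses the app arm only and fits models "separately for (a) TBI coach use, and (b) each interactive component as the main predictor". After a base model with baseline symptoms and confounders, it continues: "Then a full model with addition of the time score for one TBI Coach aspect at a time will be fitted". The decision rule is that "a significant negative coefficient of the time variable will confirm a negative association between time spent on that component and symptom severity". The component models are then compared on standardised coefficients and R-squared. Components with a strong relationship in the expected direction go on to a secondary analysis of what predicts their use.

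The H4 text gives no alpha, no multiplicity adjustment, no list of interactive components and no rule for judging H4(b) as a whole. Section 5.1 describes education, symptom self-assessment and portable skills, plus a resources section. Within the skills part, "the user is routed to any of a number of helpful skills depending on the" symptom and its severity. The protocol does not say which of these parts count as interactive, or whether a component is an app section or a single tool.

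**The concern.** The hypothesis points to one exposure fixed in advance, while the analysis supplies an uncounted set of exposures, each with its own confirmation rule. If components are app sections, the tools section is one of several models of equal standing. If they are individual tools, no model of total tools time is specified. In either case the unit of analysis and the deciding model could be chosen after the results are known.

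Two things follow. With more than one model, the chance that some component is confirmed by accident rises above that of a single designated test. And a model for one part of the tools time has less power than a model for the total, if the association runs through the total. This matters because Aim 3 and research question Q4 use component results to say which parts of the app help, and Aim 4 is meant to inform its modification and wider roll-out.

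**Working it through.** **The plan's own figure.** Section 5.6 gives no sample size or power for H4. The nearest figure is for the H1 and H2 regressions: N=148 for 80% power and N=194 for 90%, for an R-squared increment of 0.05 from 2 variables, after 10 covariates with R-squared 0.20, at alpha 0.05. With f² = 0.05/(1 − 0.20 − 0.05) = 0.0667, numerator df 2, denominator df N − 13 and noncentrality N·f², the noncentral F gives power 0.801 at N=148 and 0.902 at N=194. The stated figures reproduce.

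**Inputs for H4(b)**

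- Alpha: two-sided 0.05 per model. This is an assumption; section 5.6 states 0.05 for H1, H2 and the mediation model, not for H4.
- Favourable result: a significant negative coefficient only, so the chance per model under the null is 0.025.
- Number of component models k: not in the documents, so shown as a range. The H4(a) model for total use is not counted.
- App-arm completers: the plan's formula gives (20 × 33 + 150) × 0.60 × 0.80 = 388.8, stated as 388. Half is 194, assuming 1:1 allocation (the ratio is not stated).

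**Chance of at least one false favourable confirmation**

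Independent tests: 1 − 0.975^k. For k=2, 1 − 0.9506 = 0.0494; for k=3, 0.0731; for k=6, 0.1409.

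Test statistics with common correlation ρ: 1 − ∫ φ(z) Φ((1.96 + √ρ·z)/√(1 − ρ))^k dz.

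| k | ρ = 0 | ρ = 0.5 | ρ = 0.9 |
|---|---|---|---|
| 1 | 2.5% | 2.5% | 2.5% |
| 2 | 4.9% | 4.5% | 3.5% |
| 3 | 7.3% | 6.3% | 4.2% |
| 4 | 9.6% | 7.8% | 4.7% |
| 6 | 14.1% | 10.4% | 5.4% |

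**Power of the total against its parts (illustration)**

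Assume a partial correlation of −0.20 between total tools time and follow-up symptom score, 12 model parameters (df = 194 − 12 = 182), and noncentrality √194 · |r|/√(1 − r²).

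- Total time: 13.93 × 0.2041 = 2.84, power 0.81.
- Four equal parts with pairwise correlation ρ, the association carried by the total: each part has |r| = 0.20 × √((1 + 3ρ)/4).
- ρ = 0: |r| = 0.10, noncentrality 1.40, power about 0.29 per part.
- ρ = 0.5: |r| = 0.158, noncentrality 2.23, power 0.60 per part.
- At least one of four significant, ρ = 0: 1 − (1 − 0.285)^4 = 0.74.
- At least one of four significant, ρ = 0.5: about 0.86.

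**The case against.** Five objections carry weight.

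- **The confirmation rule is limited to the component tested.** A reader might infer that any one significant component confirms H4(b). The documents do not say so: the rule speaks of the association for that component. This stands. The gap is that no rule links the component results to H4(b).
- **The mismatch depends on the reading.** H4(b) is plural, and the reference to the tools section may only say where the components sit. If the tools section is itself a component, its total time is among the models fitted. So one cannot say that total tools time goes untested; that follows only if components are individual tools. But on either of these readings, if more than one model is fitted, no model is designated to decide H4(b).
- **Comparing components is intended.** Q4 asks about specific components relative to others, and Table 1 records time in total and by component. That is a reason to keep those models, but it does not settle which one tests H4(b).
- **The number of models may be small.** With only self-assessment and skills counted as interactive, k=2 and the chance is at most 4.9%. With one tools total, k=1 and there is no inflation. The plan's references to each component and to all component-specific models suggest more than one, but do not fix the number.
- **Splitting does not necessarily lower the chance of finding something.** A reader might infer that the multi-model route has less power overall. With uncorrelated parts it does (0.74 against 0.81). At correlation 0.5 the order reverses (about 0.86 against 0.81), and positive correlation is plausible because heavy users may use more of everything. Only the lower power of each part holds in both cases.

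The follow-on analysis adds little harm: it describes predictors of use and does not re-test symptom benefit.

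**Conclusion.** The point holds in a limited form. H4(b) is tied to the tools section, several unadjusted component models each carry their own confirmation rule, and nothing says which of them decides the hypothesis. With three to six models the chance of at least one false favourable confirmation is 4.2–14.1% over correlations from 0.9 down to 0, against 2.5% for one designated test. With two independent models it is 4.9%. In the four-part illustration each part has power of about 0.29 to 0.60, against 0.81 for the total.

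These sizes rest on an assumed two-sided 0.05 per test, an assumed number of components, 1:1 allocation, and, for power, an assumed partial correlation of −0.20 and an equal split. H4 is a non-primary, observational analysis within the app arm, and the randomised comparison in H1 is untouched. The priority is minor to moderate.

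**What to change.** In section 5.6:

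1. State that H4(b) is tested once, on total time in the tools section, at two-sided 0.05.
2. List the app components and say whether each is a section or an individual tool.
3. Report the models for other components or individual tools as exploratory, with estimates and confidence intervals. This keeps the comparison that Q4 asks for.
4. Remove the confirmation wording for those exploratory models.

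This takes a few sentences and no new data, since the app already logs time by component. The one small loss is that components other than the tools section can no longer be reported as confirmed.
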